#### **5.4.2.7 Overall Survival**

The overall survival (OS) analysis will be based on the safety population (all treated patients) only.

OS is defined as the time from study treatment initiation to death from any cause. For patients who are alive at the time of analysis data cutoff, OS time will be censored at the date the patient was last known to be alive.

Kaplan-Meier methodology will be used to estimate OS. Kaplan-Meier curves will be provided. The 95% CI of the median OS will be constructed using the Brookmeyer and Crowley method.

#### **5.4.2.8 Patient-Reported Outcomes**

The analysis of each questionnaire respectively will be performed on PRO-evaluable population only.

The EORTC Quality-of-Life Questionnaire Core 30 (QLQ-C30) and Quality-of-Life Questionnaire brain cancer module (QLQ-BN20) data will be scored according to the EORTC scoring manual ([Fayers et al. 2001](#)).

Time from study treatment initiation to cognitive symptom deterioration is defined as the time from study treatment initiation to the first time a patient's score shows a  $\geq 10$ -point increase above baseline in the following EORTC QLQ-BN20 transformed scale scores: visual disorder (items 6, 7, and 8), motor dysfunction (items 10, 15, and 19), communication deficit (items 11, 12, and 13), headaches (item 4), seizures (item 9) and drowsiness (item 14).

Time from study treatment initiation to symptom deterioration is defined as the time from study treatment initiation to the first time a patient's score shows a  $\geq 10$ -point increase above baseline in the following EORTC QLQ-C30 transformed symptom subscale scores: fatigue (items 10, 12, and 18).

Time from study treatment initiation to function deterioration is defined as the time from study treatment initiation to the first time a patient's score shows a  $\geq 10$ -point decrease from baseline in the following EORTC QLQ-C30 transformed functioning subscale scores: physical (items 1 to 5), cognitive (items 20 and 25) and role functioning (items 6 and 7) scales.

Duration of stable/improved HRQoL scores is assessed through use of the two-item Global Health Status (GHS)/ Quality-of-Life (QoL) subscale (items 29 and 30) of the EORTC QLQ-C30. Duration of Stable/Improved HRQoL scores is defined for patients

who achieve a PRO score of “improved” or “stable” as the time from the first occurrence of an “improved” or “stable” score to a “worsened” score.

Data for patients who do not achieve a 10-point change at the time of analysis data cutoff will be censored at the last time PRO data are available.

Patients post-baseline PRO scores will be classified as “improved”, “stable”, or “worsened” as follow:

- Symptom scales of the EORTC QLQ-C30 and the QLQ-BN20
  - “Improved” if a  $\geq 10$ -point of decrease is observed.
  - “Worsened” if a  $\geq 10$ -point of increase is observed.
  - “Stable” if their baseline score changes by any other
- The GHS/QoL and functional scales of the EORTC QLQ-C30:
  - “Improved” if their baseline score increases by  $\geq 10$  points,
  - “Worsen” if their baseline score decreases by  $\geq 10$  points,
  - “Stable” if their baseline score changes by any other

Time to deterioration (TTD) in BN20 scales (visual disorder, motor dysfunction, communication deficit, headaches, seizures and drowsiness), TTD in symptom (fatigue), TTD in each functioning scales (physical, role, cognitive), and duration of stable/improved HRQoL scores for GHS/QoL subscale will be analyzed using the same method as the analysis of PFS described in Section [5.4.2.4](#).

The number and proportion of patients who improve, remain stable, or worsen from baseline will be summarized by study visit.

Questionnaire completion and compliance (based on the number of patients who were expected to reach a given visit) will be summarized at each timepoint.

In the event of incomplete data, for all questionnaire subscales, if more than 50% of the constituent items are completed, a pro-rated score will be computed consistent with the scoring manuals and published validation reports. For subscales with less than 50% of the items completed, the subscale will be considered as missing.

Change from baseline scores over time in treatment/disease-related symptoms as evaluated by the EORTC QLQ-C30 and QLQ-BN20 questionnaires will be summarized descriptively including the mean change from baseline of linear-transformed scores for all subscales of the EORTC QLQ-C30 and QLQ-BN20 according to the EORTC scoring manual guideline at each assessment time point for each cohort, including progression, treatment discontinuation and follow-up. The mean and median of the absolute scores and the change from baseline will be reported for interval and continuous variables.

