6. STATISTICAL CONSIDERATIONS AND ANALYSIS PLAN

A primary study analysis that includes analyses of all efficacy endpoints and safety summaries will be conducted based on data collected up to six months after the last patient is enrolled in the study (last patient in [LPI]). The final study analysis including updated analyses of safety and efficacy endpoints will be conducted based on data collected up to 24 months after LPI.

Unless otherwise indicated, efficacy analyses will be based upon the Evaluable Patient population in each cohort consisting of all enrolled patients who received study medication and have at least two post-baseline tumour assessments for response evaluation. Analyses of safety, PRO, survival, timing of change in corticosteroid use, and time to subsequent intracranial or systemic anti-cancer treatment endpoints will be conducted based upon the Safety population in each cohort consisting of all patients who received at least one dose of study medication.

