6.4.2.1 Patient-reported Secondary Efficacy Endpoints

Time from study treatment initiation to cognitive symptom deterioration is defined as the time from baseline to the first time a patient's score shows a ≥ 10 -point increase above baseline in any of the following EORTC QLQ-BN20 transformed symptom subscale scores (whichever comes first): visual disorder, motor dysfunction, communication deficit, headaches, seizures and drowsiness.

Time from study treatment initiation to symptom and function deterioration is defined as the time from baseline to the first time a patient's score shows a ≥ 10 -point increase above baseline in any of the following EORTC QLQ-C30 transformed symptom subscale scores (whichever comes first): fatigue or physical, cognitive and role functioning scales.

Duration of Stable/Improved HRQoL scores is assessed through use of the two-item GHS/HRQoL subscale (Questions 29 and 30) of the EORTC QLQ-C30. Patients post-baseline PRO scores will be classified as "improved", "stable", or "worsened" according to a ≥ 10 -point change in the GHS/QoL, functional, and symptom scores of the EORTC QLQ-C30 and the QLQ-BN20. The number and proportion of patients who improve, remain stable, or worsen from baseline will be summarized by treatment group and study visit, at each time point, including progression, treatment discontinuation and post-study treatment.

Only patients with a non-missing baseline assessment and at least one non-missing post-baseline assessment will be included in PRO analyses. Questionnaire completion and compliance will be summarized at each time point by treatment arm.

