## **STATISTICAL ANALYSIS PLAN AMENDMENT RATIONALE**

Key changes to the SAP, along with the rationales for each change, are summarized below.

Section	Description of Change	Rationale for Change
4	Patient-reported outcome (PRO)-evaluable population added for the PRO analysis	It is stated in the protocol that “Only patients with a non-missing baseline assessment and at least one non-missing post-baseline assessment will be included in PRO analyses.” For clarify purpose, we added PRO population in the Section 4 and clarified that this population will be used for PRO analysis to ensure compliance with the protocol.
5.1	Only a subset of efficacy analysis will be done on Cohort 1	Given that the recruitment of Cohort 1 was stopped prematurely, it is no longer appropriate to produce all the efficacy analysis due to small sample size. Thus, the Statistical Analysis Plan is updated to limit the efficacy analysis.
5.3.1	No analysis on primary endpoint on Cohort 1	After the premature discontinuation of Cohort 1, it was decided to not perform the independent review of scan for patients in Cohort 1. Thus, all analyses on the primary endpoint will be performed on Cohort 2 only.
5.3.3	Adding sensitivity analysis of primary endpoints on all treated patients (safety population)	The analysis on primary endpoint is planned on evaluable population only, which excludes subjects with less than 2 scans. Excluding these subjects could lead to an inflation of the response rate by excluding the early progression or death. Therefore, we add an analysis on all treated patients to assess the bias introduced by excluding these patients.
5.3.4.1	New subgroup	Additional subgroup added to better explore the effect of demographic characteristics and clinical and biological prognostic factors on the efficacy endpoint.
5.4	Adding analysis secondary efficacy endpoints on all treated patients (safety population)	The analysis on efficacy endpoint (objective response rate [ORR], progression-free survival [PFS], and disease control rate [DCR]) are planned on evaluable population, which excludes subjects with less than 2 scans. Excluding these subjects could lead to an inflation of the response rate by excluding the early progression or death. Therefore, we add an analysis on all treated patients to assess the bias introduced by excluding these patients.

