#### 4. ANALYSIS SETS

The following populations are defined:

Population	Definition
Safety-evaluable Population	All participants received at least one dose of study treatment (e.g., atezolizumab, cobimetinib, or vemurafenib)
Evaluable Population	All enrolled patients who received study medication and have at least two post-baseline intracranial tumour assessments for response evaluation
PRO-evaluable Population	All patients who received any amount of any study medication (e.g., atezolizumab, cobimetinib, or vemurafenib) and have a baseline and at least one post baseline PRO assessment in the questionnaire of interest (EORTC QLQ-C30 or EORTC QLQ-BN20)

EORTC QLQ-C30 and QLQ-BN20=European Organization for Research and Treatment of Cancer Quality of Life questionnaire core questionnaire and brain cancer specific module; PRO=patient-reported outcome.

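### As written, SAP 5.4.2.8 puts questionnaire completion and compliance on patients selected for having returned forms; the denominator should be treated patients due the form

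*SAP*

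**What the plan says.** SAP Section 4 defines the PRO-evaluable population as treated patients who "have a baseline and at least one post baseline PRO assessment in the questionnaire of interest". SAP 5.4.2.8 opens with the rule "The analysis of each questionnaire respectively will be performed on PRO-evaluable population only". Later in the same section it plans: "Questionnaire completion and compliance (based on the number of patients who were expected to reach a given visit) will be summarized at each timepoint". That sentence does not say whether the expected patients are drawn from all treated patients or from the PRO-evaluable set, and nothing in the section takes completion and compliance out of the opening rule.

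The protocol says two things. Section 6 lists PRO with safety and survival ("Analyses of safety, PRO, survival, timing of change in corticosteroid use") among the analyses that "will be conducted based upon the Safety population in each cohort". Section 6.4.2.1, on the PRO secondary endpoints, says "Only patients with a non-missing baseline assessment and at least one non-missing post-baseline assessment will be included in PRO analyses", and 6.4.3 repeats this for the exploratory PRO endpoint. Directly after the restriction, 6.4.2.1 adds "Questionnaire completion and compliance will be summarized at each time point by treatment arm", with no population or denominator of its own.

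The SAP amendment rationale cites the 6.4.2.1 restriction and explains that "this population will be used for PRO analysis to ensure compliance with the protocol".

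**The concern.** Completion and compliance tables exist to show how many forms are missing. A set that admits only patients with a baseline form and a later form cannot show missing baseline forms. Nor can it show the patients who never returned a form after baseline.

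Three groups of secondary endpoints rest on these questionnaires: time to deterioration on the QLQ-BN20 scales, time to deterioration on the QLQ-C30 fatigue and functioning scales, and duration of stable or improved global health status. The completion table is the reader's main guide to how far those results represent the treated cohort. If it is built on the selected set, that guide is lost where selection matters most, at entry and at the first later visit.

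The SAP accepts this argument elsewhere. Its amendment rationale for 5.3.3 and 5.4 says that leaving out patients with fewer than two scans could inflate response rates, and it adds all-treated analyses to assess the bias. For PRO, the word *only* in 5.4.2.8 switches off the all-treated analysis that SAP 5.4 otherwise makes the default.

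**Working it through.** The documents give no completion or compliance figure, so there is nothing to reproduce. The check is a reading of the text followed by an illustration with assumed counts.

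**Reading**
1. Opening rule of 5.4.2.8: PRO-evaluable patients only.
2. Entry condition (SAP Section 4): a baseline form and at least one later form.
3. Completion and compliance: same section, no exemption, denominator limited to patients expected at the visit, no parent population named.
4. Steps 1 to 3 taken literally: the denominator is PRO-evaluable patients expected at the visit.

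**Baseline**

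Inputs: about 60 treated patients in Cohort 2 (protocol 4.1 gives approximately 60 enrolled; all assumed treated) and b patients without a baseline form (assumed 3 to 6).
- All treated: (60 − b)/60 = 57/60 = 95% for b = 3, and 54/60 = 90% for b = 6.
- PRO-evaluable: 100% for any b, because the form is an entry condition.

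**First later visit**

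Let E be the PRO-evaluable patients expected and e their forms. Let X be the expected patients outside the set and x their forms. The literal rate is e/E and the all-treated rate is (e + x)/(E + X). The literal rate is higher exactly when x/X < e/E, that is, when the excluded patients comply less than the included ones. Patients with no later form always contribute 0 to x. Patients missing only the baseline form may contribute 1 each.

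Assumptions: 60 treated; b without baseline; p with baseline but no later form; 4 PRO-evaluable patients who miss this visit. Then E = 60 − b − p and e = E − 4. The p patients are either all expected or all gone before the visit. The b patients either all complete this form or none does.

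| b, p | PRO-evaluable | Treated: p expected, b return none | p expected, b all return | p gone, b return none | p gone, b all return |
|---|---|---|---|---|---|
| 3, 3 | 50/54 = 92.6% | 50/60 = 83.3% | 53/60 = 88.3% | 50/57 = 87.7% | 53/57 = 93.0% |
| 3, 6 | 47/51 = 92.2% | 47/60 = 78.3% | 50/60 = 83.3% | 47/54 = 87.0% | 50/54 = 92.6% |
| 6, 6 | 44/48 = 91.7% | 44/60 = 73.3% | 50/60 = 83.3% | 44/54 = 81.5% | 50/54 = 92.6% |
| 6, 9 | 41/45 = 91.1% | 41/60 = 68.3% | 47/60 = 78.3% | 41/51 = 80.4% | 47/51 = 92.2% |

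The PRO-evaluable figure stays between 91.1% and 92.6% while the all-treated figure runs from 68.3% to 93.0%. The largest overstatement is 91.1 − 68.3 = 22.8 points. In the last column the PRO-evaluable figure is lower, by about 1 point at most.

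**The case against.** The strongest reply is that the SAP does what the protocol tells it to do. A reader who sets protocol Section 6 beside SAP 5.4.2.8 might infer that the SAP moved PRO off the Safety population on its own initiative. The documents do not support that. The restriction stands in protocol 6.4.2.1 and 6.4.3, it is worded for PRO analyses generally, and the SAP cites it as its reason. The conflict is inside the protocol, and the SAP follows the more specific text. This stands.

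Second, the completion sentence can be read as counting all treated patients expected at the visit. SAP 5.1 applies the PRO-evaluable set to PRO endpoints, and completion is not an endpoint in SAP Table 1. This also stands as a possible reading. But the opening rule covers the whole section, so the literal text points to the selected set.

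Third, a reader might infer that every later compliance figure must be inflated, or will look near-complete whatever the loss. Neither follows. One later form is enough to qualify, so a patient who then stops returning forms stays in the denominator wherever a form is expected, and that loss stays visible. Patients who left before a visit may count in neither denominator. The table also has cases where the literal figure is slightly lower.

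Finally, the protocol has safeguards: willingness and ability to complete questionnaires is an entry criterion, and protocol 4.5.10 allows staff interviews and requires a completeness check before the patient leaves. These may keep the numbers small, but they do not change what the denominator can show.

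**Conclusion.** The point holds as a defect in the stated denominator. On the literal reading, baseline completion is 100% whatever the data, and treated patients lacking a baseline form or any later form are invisible in every completion figure. That part needs no assumption beyond the reading.

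The size is illustrative. With 3 to 6 of 60 baseline forms missing, the report would show 100% where the truth is 90% to 95%. Later compliance could be overstated by many points (up to about 23 in the scenarios above) or be about unchanged, depending on whether the excluded patients were still expected and whether they returned forms. All counts of missing forms are assumed.

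It is tempting to add that non-completion in this population tracks neurological decline, progression or death. That is plausible, but the documents give no evidence for it and the point does not rest on it.

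All efficacy analyses are descriptive and no hypothesis test is affected. The change should still be made, because the table as written cannot do its job.

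**What to change.** - In SAP 5.4.2.8, state that completion and compliance are computed for each questionnaire and cohort on safety-evaluable patients who are alive and due that form at the visit. Separate denominators per questionnaire matter because, after the treatment discontinuation visit, only items 29 and 30 of the QLQ-C30 are collected (protocol 4.5.10).
- Report, per questionnaire and cohort, how many treated patients fall outside the PRO-evaluable set, split into no baseline form and no later form.
- Keep the PRO-evaluable set for change scores, time to deterioration and duration of stable or improved scores, where a baseline and a later value are needed.
- Reconcile protocol Section 6 with 6.4.2.1 and 6.4.3, so that one rule covers PRO scores and another covers completion and compliance.

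The cost is a sentence or two of SAP text, a changed denominator in one set of tables and a protocol clarification. No new data are needed. The reported completion rate may be less favourable.

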4.5.10 Patient-Reported Outcomes

To more fully characterize disease burden and clinical benefit of study treatment in patients with BRAF^{V600} mutation-positive or negative melanoma with CNS metastases, PRO data will be obtained through the EORTC QLQ-C30 and QLQ-BN20 questionnaires. Paper versions of the questionnaires will be used, and the questionnaires will be translated as appropriate in the local language.

Cobimetinib, atezolizumab, vemurafenib — F. Hoffmann-La Roche Ltd

80 / Protocol MO39136, Version 5.0

To ensure instrument validity and that data standards meet health authority requirements, questionnaires scheduled for administration during a clinic visit will be completed in their entirety by the patient before the patient receives any information on disease status and prior to the performance of non-patient reported outcome assessments and prior to atezolizumab administration (if applicable). Interviewer assessment is allowed but can only be conducted by a member of the clinic staff for patients who are unable to complete the measures on their own. Study personnel should review all questionnaires for completeness before the patient leaves the investigational site.

After the treatment discontinuation visit has occurred, patients will complete Questions 29 and 30 of the EORTC QLQ-C30 only. Post-treatment discontinuation questionnaires may be administered over the [contact] EORTC QLQ-C30

The EORTC QLQ-C30 (version 3.0) is a validated, reliable self-report measure (Aaronson et al. 1993; Fitzsimmons et al. 1999) (see [Appendix 8](#)) that is commonly used in clinical trials involving patients with metastatic melanoma (Revicki et al. 2012; Schadendorf et al. 2015). It consists of 30 questions that assess five aspects of patient functioning (physical, emotional, role, cognitive and social), three symptom scales (fatigue, nausea and vomiting, pain), global health/quality of life, and six single items (dyspnoea, insomnia, appetite loss, constipation, diarrhoea and financial difficulties) with a recall period of the previous week. Scale scores can be obtained for the multi-item scales. The EORTC QLQ-C30 module takes approximately 10 minutes to complete. A clinically meaningful difference in symptom and function deterioration is defined as a change (≥ 10 points on a 0-100 scale) in fatigue, physical functioning, cognitive functioning, or role functioning as measured by the Fatigue, Physical, Cognitive, Role Functioning scales.

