- i. Left ventricular dysfunction will be evaluated by ECHO or MUGA at screening, on Day 1 of Cycle 2 (\pm 1 week) and on Day 1 of every three treatment cycles thereafter starting at Cycle 5 (\pm 2 weeks for each), at the treatment discontinuation visit (unless evaluation performed within the previous 12 weeks showed no clinically significant findings or changes from baseline), and as clinically indicated. All patients who restart treatment with a reduced dose of cobimetinib because of a decrease in LVEF should have LVEF measurements taken after approximately 2, 4, 10 and 16 weeks (or as clinically indicated) and then resume monitoring LVEF every 12 weeks (three cycles).
- j. During the study treatment period, paper versions of the EORTC QLQ-C30 and QLQ-BN20 questionnaires will be self-administered before the patient receives any information on disease status and prior to the performance of any non-patient reported outcome assessments and prior to

Appendix 2

Schedule of Activities for Cohort 2

atezolizumab administration (if applicable). After the treatment discontinuation visit, patients will complete Questions 29 and 30 of the EORTC QLQ-C30 only. Post-treatment discontinuation visit questionnaires may be administered over the telephone.

- k. Perform a limited, symptom-directed examination including an evaluation of the oral cavity, oropharynx, head and neck (including lymph nodes), lungs, heart, abdomen and skin, at specified time points or as clinically indicated. Patients should be asked specifically about skin and vision changes as part of each physical examination. Record new or worsened clinically significant abnormalities on the Adverse Event eCRF.
- l. During the treatment period, ECG recordings must be obtained prior to the morning doses of cobimetinib and vemurafenib on Day 15 (\pm 3 days) of Cycles 1, 2, 3 and 4. Thereafter ECG recordings will be obtained on Day 15 of every three cycles (i.e. Day 15 of Cycles 7, 10, 13, etc.) (\pm 3 days); at the treatment discontinuation visit (\pm 3 days); and as clinically indicated. EGCs should be performed prior to other procedures scheduled at that same time (e.g., vital sign measurements, blood draws unless pre-authorized by the Medical Monitor) and after the patient has been resting in a supine position for at least 10 minutes.

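### Time to deterioration on ten patient-reported scales is censored at the last form, and those scales are no longer collected once the treatment discontinuation visit has passed, so the Kaplan-Meier medians are likely too long if read as deterioration-free time

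*SAP*

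**What the plan says.** SAP 5.4.2.8 defines each TTD endpoint by a score change alone. For the QLQ-BN20 scales the wording is "Time from study treatment initiation to cognitive symptom deterioration is defined as the time from study treatment initiation to the first time a patient's score" rises by at least 10 points. Fatigue uses the same rule, and the three functioning scales use a 10-point fall. Patients without such a change "will be censored at the last time PRO data are available". The endpoints "will be analyzed using the same method as the analysis of PFS described in Section" 5.4.2.4, which means Kaplan-Meier with Brookmeyer-Crowley intervals for the median.

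Protocol 4.5.10 sets the collection rule: "After the treatment discontinuation visit has occurred, patients will complete Questions 29 and 30 of the EORTC QLQ-C30 only". Footnote j of both schedules of activities (Protocol Appendices 1 and 2) repeats it. Those two questions form the global health status scale, which is not one of the ten. Both schedules place one full set of questionnaires at the discontinuation visit, which Protocol 4.6.1 puts 28 ± 7 days after the last dose.

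**The concern.** Kaplan-Meier treats a patient censored at a given time as having the same later risk as those still under observation. Here, observation of the ten scales ends because treatment has ended or the patient has died. Protocol 4.6.1 lists progression, clinical deterioration, intolerable toxicity and use of another anti-cancer therapy among the reasons for stopping. A patient who stops for brain progression is thus represented in the later part of the curve by patients still on treatment. For neurological symptoms and function that exchange is unlikely to be neutral.

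The medians are secondary endpoints in a wholly descriptive study (SAP 2), so the reported figure is the result. Protocol 3.3.6 intends these data to help oncologists explain benefits and risks to patients. A reader will naturally take a median TTD as the time for which symptoms or function stay preserved, and the SAP nowhere says that it is an on-treatment quantity. The SAP's amendment rationale recognises a related problem for response endpoints, where leaving out early progression or death could inflate the rate, and adds all-treated analyses there. It adds nothing comparable for TTD.

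**Working it through.** The plan gives no median, event count or precision for TTD, so there is no planned figure to reproduce. The check asks how far the planned estimate could lie from two other readings.

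**Inputs from the documents.** Scales: 6 + 1 + 3 = 10. Event: score change only. Last full form: the discontinuation visit. Final analysis: data to 24 months after the last patient enters (SAP 5.1). Six-month PFS in the melanoma brain-metastasis studies cited in Protocol 1.1: 29%, 46% and above 60%.

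**Assumptions, not in the documents.** Monthly forms; treatment stops at progression; one full form a month later. Monthly hazards: progression 0.12 or 0.15; death after progression 0.08 or 0.10; deterioration 0.05 or 0.08 before progression, with various values after it.

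**Step 1, hazard unchanged at 0.05.** Survival free of deterioration is exp(−0.05t), so the median is ln 2 / 0.05 = 13.9 months, seen at the month-14 form. Continuing the forms, with death censored, also gives 14. Lost collection alone causes no bias.

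Counting death changes the question. With progression hazard 0.12 and death hazard 0.08 after it, survival at 9 months is (0.12·e^(−0.72) − 0.08·e^(−1.08)) / 0.04 = 0.781. Multiplied by e^(−0.45) = 0.638, this gives 0.498, a median of about 9 months. The whole gap of 14 versus 9 comes from the endpoint definition.

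**Step 2, hazard changes after progression.** Simulation of 200,000 patients per row; medians in months, on a one-month grid.

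| Deterioration hazard before → after | Progression / death hazard | Planned KM | Forms continued, death censored | Difference | Censored in planned analysis |
|---|---|---|---|---|---|
| 0.05 → 0.05 | 0.12 / 0.08 | 14 | 14 | 0 | 69% |
| 0.05 → 0.10 | 0.12 / 0.08 | 14 | 11 | 3 | 67% |
| 0.05 → 0.20 | 0.12 / 0.08 | 12 | 8 | 4 | 64% |
| 0.05 → 0.25 | 0.12 / 0.08 | 12 | 8 | 4 | 63% |
| 0.08 → 0.16 | 0.15 / 0.10 | 9 | 7 | 2 | 60% |
| 0.08 → 0.40 | 0.15 / 0.10 | 8 | 5 | 3 | 54% |
| 0.08 → 0.04 | 0.15 / 0.10 | 9 | 12 | −3 | 64% |

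A two- to five-fold rise makes the planned median 2 to 4 months too long. In the last row, where the scale eases after stopping, it is 3 months too short.

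**Step 3, a second set anchored on the cited PFS.** Time to treatment stop is exponential with six-month PFS of 29%, 46% or 60%; forms every 28 days; on-treatment median TTD 4, 8 or 12 months; median survival after stopping 6 months; 10% of stops are deaths; follow-up 24 months. Against continued forms with death censored, the planned median differs by −1.0 to 0 months with unchanged hazard (an effect of the 28-day grid). It is 0 to 1.9 months too long at a two-fold hazard and 0 to 2.4 at four-fold. Against deterioration or death it is 0 to 4.6 months longer.

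**Step 4, a composite from the data already planned.** With deterioration, progression or death as the event, the hazards before progression add. The median is ln 2 / (0.05 + 0.12) = 4.1 months or ln 2 / (0.08 + 0.15) = 3.0 months, before rounding to visits, and does not depend on the unobserved hazard after stopping.

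**Step 5, cumulative incidence.** At 0.05 throughout, 1 − KM at 24 months is 1 − e^(−1.2) = 70%. With treatment stop as a competing event, incidence up to the stop is (0.05/0.17)(1 − e^(−4.08)) = 29%, or 31% with the extra form. This display makes deterioration look rarer.

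**The case against.** The strongest reply is that TTD is defined as a score change in both documents. Counting death or progression is then a different estimand, not the repair of an error. PFS and OS are reported separately. SAP 5.4.2.8 also summarises the proportion worsened by visit, questionnaire completion, and score changes at progression and treatment discontinuation. All of this is true. It limits the point to how the medians are read, but none of those summaries corrects a TTD curve or shows why patients were censored.

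A reader might go further than the documents allow in four ways.

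- **That collection stops with the last dose.** It does not. A full form follows about 28 days later and can record deterioration around progression. Protocol 4.3.2.3 also allows treatment, and so full forms, beyond RECIST progression in defined cases. Both features reduce the bias.
- **That most stops are for progression.** This is plausible, but the documents give no share.
- **That the bias always flatters the treatment.** It is about zero with an unchanged hazard and reverses if a scale improves off drug. Fatigue was reported in 48.7% of patients on the triplet after run-in (Protocol 1.3.2.3), and toxicity is a reason to stop.
- **That cumulative incidence should replace Kaplan-Meier to make the figures less favourable.** Step 5 shows the opposite effect on the deterioration probability.

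**Conclusion.** The point stands in limited form. Censoring on the ten scales follows treatment stop and death by design, it is probably informative, and no planned TTD analysis deals with it. The medians are likely too long if read as deterioration-free time.

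The size rests on assumed hazards. The effect of lost collection alone is about zero with no change in hazard and about 2 to 4 months with a two- to five-fold rise. The PFS-anchored scenarios are milder, at 0 to 2.4 months for two- to four-fold rises. Anything beyond that reflects the decision whether death is an event and should not be called censoring bias. A reader might also take the cross-reference to the PFS method to import progression and death as events. SAP 5.4.2.8 states its own event and censoring rule, so the reference supplies only the estimator.

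The duration of stable or improved global health status is not affected by this loss of items, because Questions 29 and 30 continue in follow-up. Error rates and sample size are untouched.

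**What to change.** In SAP 5.4.2.8:

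1. Label the present Kaplan-Meier TTD as an on-treatment analysis, with observation ending at the discontinuation visit.
2. For each of the ten scales, add a Kaplan-Meier analysis of time to deterioration, progression or death, whichever comes first.
3. Tabulate, per scale, the number censored by reason: progression, death, toxicity, other.
4. Optionally, add cumulative incidence with death and treatment stop for progression as competing events. Say that it answers a different question and gives a lower deterioration probability than 1 − KM. It should be a supplement and not the main display.

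All of this uses data already collected. The cost is SAP wording, a little programming and less favourable figures for the composite.
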